**Intraocular pressure and ocular biometrics changes after phacoemulsification in
glaucomatous patients and age matched controls, comparative study**

September 14th, 2019

Full Protocol

Background and introduction

Phacoemulsification is one of the most commonly performed surgeries in ophthalmic practice. One of the main topics of interest regarding phacoemulsification is its effect on intraocular pressure (IOP) readings whether in glaucomatous or non-glaucomatous eyes by comparing the IOP changes before and after surgery.^{1,2}

The effect of phacoemulsification on ocular biometrics as the depth of the anterior chamber (ACD) has been previously studied³. It showed significant results especially in cases of thick lenses or preoperatively shallow anterior chamber (AC) or narrow AC recess as in cases of angle closure glaucoma².

Changes in the AC angle configuration and the angle opening distance at 500 microns (AOD 500) before and after phacoemulsification have also been studied³. AOD 500 is defined by UBM as the distance of a perpendicular from the trabecular meshwork on the iris at a point 500 µm from the sclera spur⁴. In primary angle closure glaucoma patients even a clear lens extraction showed a significant increase in AOD 500 after phacoemulsification⁵. However, there is no clear evidence whether preoperative ocular biometrics could predict the amount of this IOP reduction after phacoemulsification and whether further filtering surgeries or medications will be still needed for IOP control.

Some studies have shown a significant decrease in IOP after phacoemulsification⁶, with the effect being more significant and the rate of decrease higher the narrower the angle⁷. However, other studies stated that there's a rise of IOP after cataract removal⁸ in the first week and it subsides later on. Another study actually proposed there's no

correlation between phacoemulsification and the IOP pre and postoperatively.⁹ Some studies that stated that there's lowering of IOP after phacoemulsification also showed that filtering surgery was eventually needed in the vast majority of glaucomatous cases and in few of them only cataract removal was sufficient. ¹⁰

This study aims to evaluate the changes in IOP and anterior segment parameters represented by the central ACD and the AOD 500 measured by UBM before and after phacoemulsification.

In our study we aim to establish a qualitative as well as quantitative relationship between phacoemulsification and the IOP. Also we aim at studying this relationship in non-glaucomatous eyes, open-angle and closed-angle glaucomatous eyes(only appositional type, not synechial angle closure). We want to correlate these changes to the changes in ACD and AOD at 500 pre and postoperatively to establish a quadruple relationship between phacoemulsification on one hand, and the percentage of IOP change ,ACD change and AOD at 500 change on the other hand to study the effect in various eyes and a wide spectrum of the population to earn more accurate results than previous studies.

Patients and methods

An estimation of sample size was performed considering a confidence level of at least 80% with an alpha error of 0.05. On the basis of this estimation, a total of 46 patients was considered adequate. We will include 60 patients taking into account the possibility of drop-outs in the postoperative follow up period.

This is an observational, comparative, cross sectional study that will be conducted at Kasr Alainy Cairo University Hospitals. Data collection will adhere to the tenets of the Declaration of Helsinki. Written informed consent will be obtained from all participants. Patients will be recruited from the glaucoma subspecialty and general outpatient clinics if they fulfill the following criteria; Age 40-70 years, visually significant cataracts with best-corrected visual acuity (BCVA) equal to or worse than 6/12, patients candidates for standard cataract surgeries without adjunctive procedure (e.g., pupil stretching or iris hooks). Exclusion criteria include (1) Major intraoperative orpostoperative complications from cataract surgery; (2) Peripheral anterior synechiae (PAS) detected by indentation gonioscopy; (3) Uveitis, severe retinal diseases, or congenital Anomalies, (4) History of ocular trauma or any intraocular Surgery

In addition to the routine full ophthalmological examination (Visual Acuity, Auto-refractometer, Slit lamp and fundus examination). All patients meeting the inclusion criteria will have the angle of the anterior chamber assessed by indentation gonioscopy preoperatively to detect whether the angle is opened or closed and to exclude the presence of peripheral anterior synechiae. Also intraocular pressure will be measured using a calibrated Goldman Applanation Tonometry postoperatively. Anterior Chamber Depth & lens thickness will be measured by Optical Biometry (lenstar 900) as well as measurement of the angle & lens vault using the Ultrasound Biomicroscopy (UBM) before and 1 month after cataract surgery. IOP will be measured pre- & postoperatively on day 7 and 30.

Statistical analysis plan:

All data will be entered into Excel spreadsheets (Microsoft Corporation, Redmond, WA, USA). All statistical analyses will be performed using IBM SPSS version 22.0 software (IBM Corp., Armonk, NY, USA). Descriptive statistics will be summarized as the mean \pm standard deviation for numerical data, frequencies and percentages for categorical data. The ANOVA -test and Pearson moment correlation will be used to compare the means for the numerical data and to identify correlations between them. Chi-square test will be used to compare categorical data. P-values ≤ 0.05 will be considered statistically significant.

References

- 1) MelanciaD,Abegao-Pinto L,Marquez-Nevez C:Cataract Surgery and intraocular pressure;J Ophthalmic Research 2015;53:141–148
- 2) Hsu C-H, Kakigi CL, Lin S-C,Wang Y-H, Porco T, Lin SC. Lens position parameters as predictors ofintraocular pressure reduction aftercataract surgery in nonglaucomatouspatients with open angles. Invest Ophthalmol Vis Sci. 2015; 56:7807–7813.
- 3) Ufuk Elgin, EmineSen,TulaySimsek, Kemal Tekin and PelinYilmazbas: Early postoperative effects of cataract surgery on anterior segment parameters in open-angle glaucoma and pseudoexfoliationglaucoma;Turk J Ophthalmol. 2016 Jun;46(3)95-98.
- 4) Martha Kim , Ki Ho Park, Tae-Woo Kim, Dong MyungKim:Changes in Anterior Chamber Configuration after Cataract Surgery as Measured by Anterior Segment Optical Coherence Tomography;Korean J Ophthalmol 2011;25(2):77-83.

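### The SAP has no analysis that compares the IOP-biometry relation between eye types, and does not say whether its Pearson correlations are pooled or run by eye type

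*Combined protocol and SAP*

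**What the plan says.** The aim is in the last paragraph of the Background and introduction, just before Patients and methods. It has three steps.

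- It opens with the effect of surgery on pressure: "we aim to establish a qualitative as well as quantitative relationship between phacoemulsification and the IOP".
- It extends that effect to three groups: "Also we aim at studying this relationship in non-glaucomatous eyes, open-angle and closed-angle glaucomatous eyes". Closed-angle eyes are limited to the appositional type.
- It then brings in the biometry: "We want to correlate these changes to the changes in ACD and AOD at 500 pre and postoperatively". The link from this step to eye types is loose; the stated purpose is "to study the effect in various eyes and a wide spectrum of the population".

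The Statistical analysis plan covers all numerical data in one sentence: "The ANOVA -test and Pearson moment correlation will be used to compare the means for the numerical data and to identify correlations between them". The only decision rule is "P-values ≤ 0.05 will be considered statistically significant". The SAP has no regression with eye type, no interaction, no test comparing correlations, no confidence interval for a correlation, and no statement on whether Pearson is pooled or by group.

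Patients and methods gives 46 patients as adequate and 60 to be enrolled, without a split by eye type.

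**The concern.** The study is titled as a comparison of glaucomatous patients and controls, and it wants the link between IOP change and anterior-segment change described in differing eyes. Neither way of running Pearson does that well.

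Run by eye type, it gives one P value per group and no comparison of the groups. A significant coefficient in closed-angle eyes beside a non-significant one in controls would make an attractive headline, yet with 15 to 20 patients per group a mixed pattern of this kind can arise often when the relation is the same everywhere.

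Run on all patients together, it can show a correlation only because one eye type has both a larger IOP fall and a larger biometric change, with no relation among patients of the same type.

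What is at stake is the interpretation of the correlation results. The comparison of mean IOP change is not affected.

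**Working it through.** **Inputs from the documents.** Three eye types; 46 patients adequate and 60 enrolled; P ≤ 0.05.

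**Assumptions.** Two-sided tests, one eye per patient, bivariate normal data, and splits of 15/15/16 (46 analysed) or 20/20/20 (60 analysed). The documents give no split and no expected correlation, so a range of r is shown.

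**The plan's own figure.** The 46 cannot be reproduced, because no effect size, SD or target test is given. At two-sided 0.05, and reading the stated 80% as power, one pooled correlation of 0.40 needs ((1.960 + 0.842) / atanh 0.40)² + 3 = (2.802 / 0.4236)² + 3 = 46.7. Two groups of 23 with a standardised difference of 0.83, or a three-group ANOVA with f = 0.47, fit equally well. The figure therefore does not reveal which analysis was meant.

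**By eye type: threshold.** The smallest significant coefficient is t / √(t² + n − 2). For n = 15, t = 2.160 gives 0.514; for n = 16, t = 2.145 gives 0.497; for n = 20, t = 2.101 gives 0.444.

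**By eye type: chance of a mixed verdict (some significant, some not) when the true r is the same in all three.** With group powers p1, p2 and p3 from simulation, this is 1 − p1·p2·p3 − (1 − p1)(1 − p2)(1 − p3).

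- 15/15/16 at r = 0.5: powers 50%, 50% and 53%; all significant 13.3%, none 11.7%; mixed 100 − 13.3 − 11.7 = 75.0%.
- 20 per group at r = 0.4: power 43.1%; 1 − 0.431³ − 0.569³ = 1 − 0.080 − 0.184 = 0.736.

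| True r in every eye type | 15/15/16 | 20/20/20 |
|---|---|---|
| 0.2 | 30% | 35% |
| 0.3 | 48% | 57% |
| 0.4 | 67% | 74% |
| 0.5 | 75% | 69% |
| 0.6 | 62% | 41% |
| 0.7 | 31% | 13% |

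An uneven split of 23/15/8 at r = 0.5 gives 80%. A model testing equal slopes rejects in about 5% of such cases when the spread is also equal.

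**Worked example, 20 per group.** r = 0.50 gives P = 0.025 and r = 0.40 gives P = 0.081. Compared directly, z = (0.5493 − 0.4236) / √(2/17) = 0.1257 / 0.3430 = 0.37, so P = 0.71.

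**Pooled.** Take no relation within any eye type, three equal groups, and one group shifted by 1 SD on both variables. The between-group variance and covariance are each (1/3)(2/3) = 2/9, so the pooled r is about (2/9) / (1 + 2/9) = 2/11 = 0.18. In simulation at 20 per group it is significant about 30% of the time.

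**Power of a direct comparison (interaction F test).** For r = 0, 0 and 0.7: about 52% at 46 patients and 65% at 60. For r = 0, 0 and 0.4: about 17% to 18% at 46 and 22% at 60.

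**Slopes versus correlations.** With r = 0.5 in every group but the biometric SD doubled in one, the interaction test rejects about 17% (46 patients) to 22% (60), because the slopes then do differ.

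**The case against.** Several stronger readings are tempting, and the documents do not support them.

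- *The plan sets out to test whether the IOP-biometry relation differs by eye type.* In the sentence naming the three types, the relationship meant is that of surgery with IOP. The biometry comes in the following sentence. The Background remark "with the effect being more significant and the rate of decrease higher the narrower the angle" reports that IOP fall varied with angle width in earlier studies, which a single correlation could address; it does not say that the slope varies by diagnosis.
- *The SAP tests nothing but correlations.* It also plans ANOVA. If that is run across eye types (the grouping is not stated), it directly compares mean IOP change, which is what the three-type sentence asks for.
- *Pearson will be run by eye type and its P values will be read as differences.* Neither is written. Pooling fits the text equally well, and then the mixed-verdict figures do not apply.

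These limits stand. It also stands that the mixed-verdict chance depends heavily on the unknown r and peaks near 0.4 to 0.5; at r = 0.8 it is only about 7% with 15 per group and 1% with 20. Finally, a direct comparison will often be inconclusive at this size.

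None of this closes the gap. ANOVA of means says nothing about the relation between two changes, and pooling replaces one problem with another. Low power is a reason to report intervals and be cautious, not to rely on separate P values, which do not test a difference at all.

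**Conclusion.** The point holds in limited form. The plan wants IOP change related to ACD and AOD 500 change in differing eyes, and its only tool for that is a Pearson coefficient of unstated grouping with a significance threshold. By eye type, differences in significance may be taken for differences between eye types; over r = 0.2 to 0.7 and the splits tried, a mixed verdict under identical relations has a chance of about 13% to 80%. Pooled, the coefficient mixes two kinds of association.

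A reader might infer that a false contrast is the expected outcome, or that the study is invalid. The documents support neither: the first depends on an r, a split and a by-group analysis that they do not state, and the comparison of means is unaffected. This is a cheap improvement to the SAP that guards against a misleading conclusion about the correlations.

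**What to change.** - State whether correlations are pooled or by eye type.
- For each biometric (ACD change, AOD 500 change), fit one linear model of IOP change on biometric change, eye type and their interaction. Report the slope in each eye type with its 95% CI, and the interaction P value.
- If an interaction is not shown, report the common within-group slope adjusted for eye type, and say that no difference was shown, not that the relations are equal.
- State that eye types will be said to differ in this relation only on the interaction or on the CI for a slope difference, never on separate P values. Label the comparison exploratory.

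The cost is one model per biometric in the SPSS software already planned, plus a few lines of SAP text; no extra patients or measurements are needed. Two downsides should be stated in the SAP. The model compares slopes, which can differ when correlations do not if the spread differs by eye type. Power is low at 46 to 60 patients, so some apparent findings confined to one eye type could no longer be claimed.

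### The aim can be read as calling for percentage change in AOD 500, which is undefined or unstable when the preoperative gap is zero or very small, and the SAP defines no change variable

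*Combined protocol and SAP*

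**What the plan says.** The only place that names a scale for the change measures is the aim paragraph just before Patients and methods, which seeks a relationship between surgery and "the percentage of IOP change ,ACD change and AOD at 500 change on the other hand". Earlier in the same sentence the wording is plain: "We want to correlate these changes to the changes in ACD and AOD at 500 pre and postoperatively". The general aim closing the main part of Background and introduction is plain too: "This study aims to evaluate the changes in IOP and anterior segment parameters represented by the central ACD and the AOD 500".

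Background and introduction defines AOD 500 as "the distance of a perpendicular from the trabecular meshwork on the iris at a point 500 µm from the sclera spur". The aim lists non-glaucomatous eyes, open-angle glaucoma and "closed-angle glaucomatous eyes(only appositional type, not synechial angle closure". Under Patients and methods the angle is "assessed by indentation gonioscopy preoperatively to detect whether the angle is opened or closed", and the plan calls for "measurement of the angle & lens vault using the Ultrasound Biomicroscopy (UBM) before and 1 month after cataract surgery".

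The Statistical analysis plan gives mean ± SD, ANOVA, Pearson correlation and chi-square. It has no change formula, no denominator, no transformation or rank method, and no rule for a zero baseline. No preoperative AOD 500 value appears anywhere.

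**The concern.** In the aim, the words about a percentage stand at the head of a three-item list. An analyst who follows them literally would compute 100 × (post − pre) / pre for AOD 500. The denominator is then the preoperative gap between meshwork and iris, in a study that deliberately includes eyes whose iris lies against the meshwork.

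Two things can go wrong. An eye with a preoperative reading of 0 has no percentage change and leaves the analysis without any rule having been written for it. An eye with a reading slightly above 0 receives a very large value that reflects its baseline, and the error in that baseline, more than the opening achieved. Means, SDs, ANOVA and Pearson correlation are all sensitive to a few extreme values and to very unequal spread between groups. At stake is the relation between IOP change and angle change, which the aim sets out to establish.

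**Working it through.** **Is there a figure to reproduce?** No. The plan states no AOD 500 value and no change formula. Its sample size (46, enrolled as 60) comes without an effect size, SD, test or allocation and does not bear on this point. All baselines and gains below are assumptions.

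**Step 1. Sensitivity to the denominator.** Percentage change = 100 × gain / baseline, with an assumed gain of 150 µm throughout:

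| Preoperative AOD 500 (µm) | Calculation | Percentage change |
|---|---|---|
| 250 | 100 × 150/250 | 60% |
| 100 | 100 × 150/100 | 150% |
| 50 | 100 × 150/50 | 300% |
| 25 | 100 × 150/25 | 600% |
| 10 | 100 × 150/10 | 1500% |
| 0 | division by zero | undefined |

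The absolute change is 150 µm in every row.

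**Step 2. Sensitivity to reading error.** Let the preoperative reading be wrong by ±20 µm (assumed) and the postoperative value be exact at baseline + 150 µm.

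- Baseline 250, postoperative 400: (400 − 270)/270 = 48% to (400 − 230)/230 = 74%.
- Baseline 50, postoperative 200: (200 − 70)/70 = 186% to (200 − 30)/30 = 567%.
- Baseline 25, postoperative 175: (175 − 45)/45 = 289% to (175 − 5)/5 = 3400%.

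In absolute units the same error moves each result only between 130 and 170 µm.

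**Step 3. Spread between groups.** Simulation with three groups of 20 eyes, baselines below 0 set to 0. Assumed open-angle baseline 250 ± 50 µm and gain 80 ± 50 µm; assumed closed-angle gain 150 ± 50 µm. The undefined share can be checked by hand as the normal probability below 0, for example P(Z < −20/20) = 16%.

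| Assumed closed-angle baseline (µm) | Closed-angle eyes undefined | SD of percentage change, closed ÷ open (median) |
|---|---|---|
| 20 ± 20 | 16% | 67 |
| 50 ± 30 | 5% | 20 |
| 100 ± 40 | under 1% | 5.5 |
| 120 ± 30 | 0% | 2.7 |

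These two columns do not depend on how IOP relates to the angle. They depend heavily on the assumed baseline.

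**Step 4. Effect on the correlation with IOP change.** This does depend on what is assumed to be true. Take 15 eyes in each of three groups, with baselines 0.35, 0.30 and 0.05 mm (SD 0.10, 0.10, 0.04), gains 0.08, 0.10 and 0.20 mm (SD 0.06), a true correlation of 0.5, and a smallest readable gap of 0.01, 0.02 or 0.03 mm.

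- If IOP change follows opening in mm: analysis in mm detects it (P ≤ 0.05) in about 96% of studies, and analysis as a percentage in about 46% to 71%. Raising the closed-angle baseline to 0.12 mm (SD 0.03) lifts the percentage analysis to about 80%.
- If IOP change follows percentage opening: the result reverses, with about 97% for the percentage and about 43% to 72% for mm.
- If IOP change follows the log ratio: the percentage again does better, about 92% to 95% against 72% to 81%.

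Step 4 therefore measures the cost of a mismatch between the analysis scale and an assumed truth. It is not a general power loss from using percentages. The case for absolute units rests on Steps 1 to 3.

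**The case against.** The strongest reply is that the plan never commits to a percentage for AOD 500. The phrase also parses as three separate items with the percentage attached to IOP alone; both other statements of the aim speak of plain changes; and the SAP mentions percentages only for categorical data. This stands as far as it goes: the percentage reading is natural but not settled. It does not dispose of the point, because the plain wording does not say absolute either and nothing in the SAP decides between them.

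Three stronger claims are tempting, and the documents do not support them.

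- A reader might infer that appositional closure fixes the preoperative AOD 500 at or near zero by definition. It does not. Closure is a gonioscopic finding with no AOD 500 threshold, while AOD 500 is "the distance of a perpendicular from the trabecular meshwork on the iris at a point" 500 µm from the scleral spur. An eye can be graded closed and still show a gap there. Zero or very small values are possible; how common they will be cannot be read from the plan.
- A reader might infer that the study would lose up to half its power. Step 4 shows that this holds only if IOP change follows absolute opening, that it shrinks at larger baselines, and that it reverses under other assumptions.
- A reader might infer that the closed-angle group is the one the study most needs. The aim lists the three eye types without ranking them. The background does report a greater IOP effect in narrower angles, but which group matters most is a judgement.

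**Conclusion.** The concern holds in conditional form. The aim can naturally be read as asking for percentage change in AOD 500, and the SAP supplies no other definition. On that reading the measure has no value for an eye with a preoperative reading of 0 and is unstable for small readings: 300% at 50 µm and 1500% at 10 µm for the same assumed 150 µm gain that gives 60% at 250 µm. Mean ± SD, ANOVA and Pearson correlation do not guard against this.

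The size depends on preoperative AOD 500 values that the documents do not give. It is severe if closed-angle baselines are around 20 to 50 µm and modest at about 100 µm or more. If the percentage was meant for IOP only, what remains is an undefined change variable that needs a sentence. Either way the same repair settles it. The instability concerns AOD 500; nothing in the documents suggests ACD baselines near zero, and ACD enters only because the same phrase leaves its scale open.

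**What to change.** In both the aim and the Statistical analysis plan:

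1. Define AOD 500 change and ACD change as the postoperative value minus the preoperative value, in µm or mm.
2. Keep any percentage change for IOP only, and say so.
3. State that a preoperative AOD 500 of 0 is entered as 0 and that the eye stays in every AOD 500 analysis.

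This needs no new measurements and no more patients, and is best done before any data are analysed. The one small downside is that there will be no percentage figure for AOD 500 to compare with papers that report one.

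### The plan enrols 14 extra patients to cover drop-out, but its named methods cannot use the day 7 IOP of a patient lost before day 30

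*Combined protocol and SAP*

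**What the plan says.** Under Patients and methods, the sample-size paragraph states that "a total of 46 patients was considered adequate" and continues: "We will include 60 patients taking into account the possibility of drop-outs in the postoperative follow up period". No drop-out rate is given.

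The measurement paragraph sets the visits: "IOP will be measured pre- & postoperatively on day 7 and 30". Optical biometry and UBM are done "before and 1 month after cataract surgery", so they have no day 7 value.

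The Statistical analysis plan says: "The ANOVA -test and Pearson moment correlation will be used to compare the means for the numerical data and to identify correlations between them". The type of ANOVA is not stated. Chi-square is also named, but for categorical data. The section defines no analysis set and no method for missing values, and it plans no comparison of lost with retained patients.

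The comparison of interest is across "non-glaucomatous eyes, open-angle and closed-angle glaucomatous eyes". The background notes that "other studies stated that there's a rise of IOP after cataract removal⁸ in the first week and it subsides later on".

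**The concern.** Over-enrolment answers the question of how many patients remain. It does not address whether those who remain resemble those who left.

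A patient seen on day 7 and then lost has a valid postoperative IOP change, and that reading says something about the missing day 30 value. The usual forms of the named methods do not use it for day 30:

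- One-way ANOVA on day 30 IOP, or on change to day 30, ignores day 7.
- Classical repeated-measures ANOVA drops any patient with a missing visit.
- Pearson correlation needs both values.

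The day 30 result therefore describes only those who came back. At stake are the day 30 IOP change, the apparent course from day 7 to day 30 (a question the background itself raises) and, under narrower conditions, the contrast between diagnosis groups.

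**Working it through.** **1. The drop-out margin.** Inputs from Patients and methods: 46 and 60.

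- 60 − 46 = 14, and 14/60 = 23.3%.
- The usual inflation, 46/(1 − d) rounded up, gives 60 for d from about 22.0% to 23.3%.
- The 46 itself cannot be reproduced, because no effect size, SD, endpoint, test or group allocation is given. The point does not depend on it.

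**2. Bias in the completers' day 30 mean.** The inputs are assumptions, not from the documents:

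- SD of IOP change 4 mmHg at each visit, with no true difference between day 7 and day 30.
- Day 7 to day 30 correlation ρ of 0.4, 0.6 or 0.8.
- All 14 lost after day 7, with the relative chance of loss multiplied by 2 or 3 per SD of higher day 7 IOP (called the odds ratio, OR).

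The bias is ρ × SD × s, where s is the mean day 7 z-score of those retained. Simulation with n = 60 gives s of about −0.17 at OR 2 and −0.24 at OR 3. For example, 0.6 × 4 × (−0.17) = −0.41, against −0.40 simulated.

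| OR | ρ = 0.4 | ρ = 0.6 | ρ = 0.8 |
|---|---|---|---|
| 1 | 0 | 0 | 0 |
| 2 | −0.27 | −0.40 | −0.54 |
| 3 | −0.37 | −0.59 | −0.77 |

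Units are mmHg. A negative value means the completers look better than the full cohort. A regression-type estimate that also uses the day 7 values of those lost is within 0.01 mmHg of the truth in every cell, with essentially the same spread. For scale, the standard error of a mean on 46 patients is 4/√46 = 0.59 mmHg.

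A separate check used a logistic loss model with OR 1.5 to 3 and ρ of 0.3 to 0.7. It gave 0.02 to 0.15 SD, which is 0.1 to 0.6 mmHg at SD 4.

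**3. Apparent course from day 7 to day 30 (true difference zero).** The direction depends on which ANOVA is meant.

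- *Visit by visit:* day 7 uses all 60 (bias 0) and day 30 uses 46, so the difference equals the table above, a spurious fall of about 0.3 to 0.8 mmHg.
- *Complete sets:* both visits use the same 46. The difference is SD × s × (ρ − 1). At OR 2 this is 4 × (−0.17) × (ρ − 1) = +0.41, +0.27 and +0.14. At OR 3 it is 4 × (−0.24) × (ρ − 1) = +0.58, +0.38 and +0.19. This is a spurious rise, because loss selects more strongly on day 7 than on day 30.

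**4. Contrast between diagnosis groups.** Assume 20 per group (60/3; the allocation is not stated).

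- Loss that differs by group but is random within group (10 of 20 against 2 of 20): bias about 0.
- IOP-related loss that acts alike in all groups: at most 0.03 mmHg, which is simulation noise.
- IOP-related loss of 8 of 20 against 2 of 20, OR 2 to 3: bias about 0.4 to 1.0 mmHg. The standard error of that contrast is 4 × √(1/12 + 1/18) = 1.49 mmHg.

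**5. If loss depends on the unseen day 30 value** (OR 2 per SD, ρ of 0.3 to 0.7): completers are off by about 0.15 SD, and the model using day 7 is still off by 0.08 to 0.14 SD. At SD 4 that is 0.6 against about 0.3 to 0.55 mmHg.

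**The case against.** The strongest reply is that the size of the bias comes entirely from assumptions. The protocol speaks only of a possibility of drop-outs. It gives no rate, no timing and no reason to think that patients with higher IOP are the ones lost. Placing all 14 losses after day 7 and letting them depend only on day 7 IOP favours the mixed model, whose near-zero bias then follows by construction. Most of the pooled-mean biases are also below one standard error. All of this stands, and it makes the figures an illustration of a risk rather than an estimate.

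Three stronger readings are tempting, and the documents do not support them:

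- *That the plan forecasts 23% loss.* It does not. That figure is a recruitment margin.
- *That recruiting from glaucoma and general clinics, with possibly unequal loss, by itself distorts the group comparison.* It does not. Loss that is random within group leaves the contrast unbiased.
- *That selective loss would imitate the early rise that later subsides.* This holds only for visit-by-visit analysis. On complete sets the artefact runs the other way, and the plan does not say which ANOVA is meant.

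It is also fair to say that the remedy does not reach the planned correlations with ACD and AOD 500, which have no day 7 measurement.

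None of this removes the core point. The plan provides for postoperative loss, collects a reading that could partly correct for it, and names methods that cannot use that reading.

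**Conclusion.** The point holds in limited form, as something that should be fixed rather than a fatal flaw. The plan leaves room to lose up to 14 of 60 patients, and its methods for numerical data restrict day 30 results to attenders. If loss is unrelated to IOP, there is no bias. If loss is related to day 7 IOP, the pooled day 30 mean is too favourable by about 0.3 to 0.8 mmHg under the stated assumptions, and the day 7 to day 30 course is distorted in a direction set by the unspecified type of ANOVA. The group contrast, which is the main aim, is at risk only if IOP-related loss differs in amount or strength between groups. It is then biased by about 0.4 to 1.0 mmHg in the 8-against-2 example. A model using all observed IOP removes the part of the bias that observed readings explain, and no more.

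**What to change.** In the Statistical analysis plan:

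- Analyse IOP change at day 7 and day 30 together in one linear mixed model (SPSS MIXED) with diagnosis group, visit and group by visit, and an unstructured covariance. Include every operated patient with at least one postoperative IOP, and take the day 7 and day 30 estimates from this model.
- Because the groups are not randomised and may differ in baseline IOP, report the model with and without baseline IOP, and state in advance which is primary.
- Say how the exclusion for major intraoperative or postoperative complications applies to this analysis set, since it also removes patients after enrolment.
- Add a table by group of losses by visit, with baseline and day 7 IOP for lost and retained patients.
- State that the correlations among percentage IOP change, ACD change and AOD 500 change apply to 1-month attenders only.

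The cost is SAP wording, one model and one table, with no added visits, patients or measurements. There are three downsides. The model corrects only loss explained by observed data. It does not help patients lost before day 7. The IOP and biometry analyses will rest on different numbers of patients, which needs a footnote.
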